#### 14.4 Serious Device Related Adverse Event

Any sign, symptom, or disease in a study subject that occurs during the course of a clinical study that is determined by the investigator to have a causal relationship or possible causal relationship with the investigational device and meets the definition of serious as described above.

#### 14.5 Unanticipated Adverse Device Event (UADE)

Any serious adverse effect on health and safety or any life-threatening problem or death caused by, or associated with a device, if that effect, problem, or death was not previously identified in nature, severity, or degree of incidence in the investigational plan, or any other unanticipated serious problem associated with a device that relates to the rights, safety, or welfare of subjects.

As with any investigational device, there may be risks associated with the use of the AeroForm System that are unknown. If any serious unanticipated device related adverse events occur during this study, they will be immediately (24 hours from knowledge of event) reported to the IRB and Sponsor in accordance with applicable regulations.

The following table summarizes the potential adverse events in this study:

**Table 4 Adverse Events**

Event	Definitions/Criteria
Surgical Site Inflammation	Severe erythema (redness), edema (swelling), and tenderness at the surgical site.
Bruising	Severe bruising (purple discoloration) at the surgical site
Bleeding	Significant bleeding at the surgical site requiring medical intervention or return to the operating room.
Hematoma	Collection of blood under the skin at the surgical site requiring medical intervention or return to the operating room for evacuation
Seroma	Collection of serous fluid under the skin at the surgical site requiring medical intervention or return to the operating room for drainage.
Fever	Post-operative fever of > 38.5° C (101.3° F)
Surgical Site Infection	Infection at the surgical site requiring medical treatment
Systemic Infection or Sepsis	Positive blood cultures and clinical diagnosis of sepsis
Pain	Severe pain requiring additional medical intervention or follow up
Sensory Loss	Significant numbness (paresthesia) at the surgical site
Tissue damage	Tissue thinning, necrosis, sloughing, (due to due to poor vascularization)
Wound dehiscence	Open wound at the expansion site
Extrusion	Extrusion at intended pressure, not wrinkle edge
Erosion	Exposure of the implant despite a lack of excessive pressure
Capsular contracture	Contracture of the pocket preventing adequate expansion
Malposition	Displacement of the implant due to migration
Reoperation	Any unplanned return to the operating room including device removal and/or replacement.
Other	Any other new sign or symptom that is reported by the subject during their enrollment in the study. Record by body system/event, i.e., Cardiac/Chest Pain, Pulmonary/Pneumonia that in the opinion of the investigator constitutes an adverse event.

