### **4.2 Secondary Outcome Measures**

The safety of the device will be evaluated by:

- Device related adverse events
- All adverse events, regardless of whether serious or there is a causal relationship to the device.
- Serious device related adverse events
- All serious adverse events, regardless of whether there is a causal relationship to the device.
- Device malfunctions leading to expander removal and/or replacement.

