## **14 Adverse Events**

During the course of the study, adverse event data will be collected according to the definitions below:

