### **14.1 Adverse Event (AE)**

An adverse event is defined as any untoward medical occurrence in a subject, regardless of whether the event is related to the device. All adverse events occurring during the subject's participation from the time of implant to the time of explant of the expander(s) will be recorded on the AE Case Report Form. Data collected will include a description of the event, onset date, management or treatment/intervention required, outcome, and resolution date (or whether the AE is ongoing). Subjects with adverse events that are ongoing should be followed until resolution of a serious AE and/or if they may be device related. All AEs will be reviewed and assessed by the investigator for severity (Table 2) and causal relationship to the device (Table 3). The investigator will also determine whether the AE meets the definition of serious as described in Section 14.2.

The investigator will use the following definitions to rate the severity of each AE:

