**Table 2 Adverse Event Severity Rating**

Severity	Description
Mild	
 
• Awareness of a sign or symptom that does not interfere with the subject's usual activity or is transient, resolved without treatment and
 
• no sequelae
 

Moderate	
 
• Interferes with the subject's usual activity and/or
 
• requires symptomatic treatment
 

Severe	
 
• Symptom(s) causing severe discomfort and
 
• significant impact on the subject's usual activity and
 
• requires treatment
 

**Note: Adverse events that are rated as severe are not the same as serious adverse events. For example a subject may have severe pain may require treatment but not lead to a 'serious' event as defined below.**

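### Table 4 sets severity, treatment or temperature criteria for nine adverse event terms while Section 14.1 requires every untoward occurrence to be recorded, and nothing says which governs the all-adverse-events outcome

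*Combined protocol and SAP*

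**What the plan says.** Section 14 opens with the collection rule: "During the course of the study, adverse event data will be collected according to the definitions below". Two sets of definitions follow.

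- **Section 14.1.** "An adverse event is defined as any untoward medical occurrence in a subject, regardless of whether the event is related to the device". The recording rule is equally broad: "All adverse events occurring during the subject's participation from the time of implant to the time of explant of the expander(s) will be recorded". The investigator then grades each event for severity and for relationship to the device.
- **Table 2.** The grades are mild, moderate and severe. Mild begins with "Awareness of a sign or symptom that does not interfere with the subject's usual activity or is transient, resolved without treatment".
- **Table 4 (end of Section 14.5).** It is introduced as a summary of potential adverse events, but its second column is headed *Definitions/Criteria*. Pain is "Severe pain requiring additional medical intervention or follow up" and bruising is "Severe bruising (purple discoloration) at the surgical site". Inflammation must also be severe, and sensory loss must be significant numbness.

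The secondary safety outcomes in Section 4.2 include "All adverse events, regardless of whether serious or there is a causal relationship to the device".

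**The concern.** The two definitions classify the same event differently. A coordinator who works from Section 14.1 records moderate post-operative pain. One who works from Table 4 can reasonably leave it out, because the row for pain asks for more. The text has no order of precedence and no exemption for expected post-surgical signs.

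At stake is the meaning of a named safety outcome. Used as an entry rule, Table 4 can only remove events that Section 14.1 would admit, so any error runs towards fewer events for the investigational device. If some sites use one rule and some the other, the pooled rate mixes two definitions.

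**Working it through.** The protocol states no expected adverse event rate, so there is no figure to reproduce. The check is a comparison of text, followed by the little arithmetic that the documents support.

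**1. How far the criteria reach.** Table 4 has 17 named rows plus *Other*.

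| Type of criterion | Rows | Count |
|---|---|---|
| Severe | inflammation, bruising, pain | 3 |
| Significant | sensory loss | 1 |
| Medical intervention or return to the operating room | bleeding, hematoma, seroma | 3 |
| Medical treatment | surgical site infection | 1 |
| Above 38.5 °C | fever | 1 |

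3 + 1 + 3 + 1 + 1 = 9 of 17 rows. Rows such as malposition and wound dehiscence carry no such criterion.

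**2. The same event under each rule.**

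- *Pain that interferes with activity and needs symptomatic treatment, but is not judged severe.* Section 14.1: recorded, Table 2 moderate. Table 4 pain row: not met.
- *Seroma that resolves untreated, with no sequelae.* Section 14.1: recorded, and can be Table 2 mild. Table 4 seroma row: not met.
- *Marked purple bruising that needs no treatment.* Section 14.1: recorded. Table 4: can be met. Table 2: cannot be graded severe, because that grade requires treatment.

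The first two show the conflict. The third shows that severe in Table 4 is not the Table 2 grade.

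**3. Whether the *Other* row closes the gap.** It covers any other new sign or symptom, which most naturally means signs not already listed, and it depends on the investigator's opinion. It may catch some lesser events, but not reliably.

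**4. Size.** Let *u* be the share of women whose only untoward occurrences fall below the Table 4 criteria, and *t* the share of women at sites that use Table 4 as the entry rule. Assume *u* is the same at all sites. The shortfall in the proportion with any adverse event is

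shortfall = *u* × *t*.

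- All sites follow Section 14.1 (*t* = 0): no shortfall.
- All sites follow Table 4 (*t* = 1): shortfall *u*, with no site difference from this cause.
- Sites differ (0 < *t* < 1): shortfall between 0 and *u*, and recording differs between sites.

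Neither *u* nor *t* is in the documents. What can be fixed is the unit. With up to 60 subjects (Section 6), one woman dropped is 1/60 = 1.7 percentage points. With up to 7 sites (Synopsis), an average site holds 60/7 = 8.6 women. If events are counted instead of women, each unrecorded event lowers the count by one, whatever else the woman had.

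**The case against.** The strongest reply is that Section 14.1 contains the only explicit recording rule, while Table 4 is introduced as a summary within the section on unanticipated events. Nothing says that an event below its criteria goes unrecorded. Formal training aimed at uniform data collection (Section 16), monitoring (Section 17) and experienced sites make divergence less likely. The case report forms (Appendix C) are not available to us and might settle the matter. This stands as a reason to say *may*. It does not remove the conflict, because the opening of Section 14 refers to the definitions in that section and Table 4 offers criteria under that label.

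Four stronger readings are tempting, and the documents do not support them.

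- *The rate will be understated and will vary by site.* Both depend on sites using Table 4 as a gate. They are also separate outcomes: uniform use of Table 4 gives the first without the second.
- *Mild and moderate grades cannot occur for these terms.* They can, as the bruising example shows, and they remain fully usable for rows without a criterion.
- *Device related pain from over-expansion will be missed.* Section 14.3 defines a device related event as any sign, symptom or disease with at least a possible causal link, with no severity threshold. Section 14.6 requires events at least possibly related to reach the sponsor within 24 hours. Pain is also scored on an 11-point scale at the start of home expansion, one week later and at completion (Sections 11.4 and 11.5). That scale assigns no causality and does not cover bruising, inflammation or numbness.
- *The shortfall is tens of percentage points.* Assuming *u* of 20% to 60% and 3 of 7 equal-sized sites using Table 4 gives 0.20 × 3/7 = 8.6 to 0.60 × 3/7 = 25.7 points. Every input there is an assumption, and the affected women must have no other recorded event. It illustrates the formula and is not an estimate.

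It is also fair that the consequence is bounded. This is a single-arm continued access study, the protocol text states no safety threshold, and the primary outcome counts failures by removal or replacement of the expander, which these recording criteria do not change.

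**Conclusion.** The contradiction is real and can be read directly from Sections 14 and 14.1 and Table 4. Because the protocol does not say which definition governs, lesser events may go unrecorded, the rate for the all-adverse-events outcome may be understated, and recording may differ between sites. The direction, if there is an error, is towards fewer events. The size cannot be stated from the documents: it runs from zero, if every site follows Section 14.1, to the unknown share *u*, if every site follows Table 4. The point should be corrected because a stated criterion, applied as written, gives a low count for a named secondary safety outcome. It does not threaten the primary outcome, and Section 14.3 already covers device related events without a severity threshold.

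**What to change.** Reconcile Section 4.2, Section 14.1, Table 2 and Table 4 in one of two ways.

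1. **Preferred.** Add under Table 4 that it supplies terms and coding criteria and is not a recording threshold, that every untoward occurrence is recorded and graded under Section 14.1, and that events meeting the Table 4 criteria are reported as a separate line.
2. **If the threshold is intended.** Rename the outcome in Section 4.2 (and in the Synopsis) as adverse events meeting Table 4 criteria, and state that device related events under Section 14.3 are recorded regardless of severity.

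Either is a sentence or two of text, with no change to sample size, visits or treatment. The cost of the first is some more mild events on the case report form. The second keeps the form shorter, but the study then no longer reports an all-adverse-events rate.

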### ***Overfilling***

The reservoir inside the AeroForm Tissue Expander releases a controlled amount of CO2 when the button on the hand-held controller is activated. AirXpanders recommends that the physician and the patient expand gradually. Expansion progress should be assessed by the physician based on tissue laxity, perfusion and firmness of the expander.

Note that the AeroForm Tissue Expander has a non-distensible inner liner which cannot be inflated beyond the labeled volume. Dosing beyond the labeled volume or too rapid tissue expansion may lead to increases in the relative expander pressures, possibly leading to discomfort, wound dehiscence, tissue damage or rupture of the expander. If that occurs, stop expansion immediately.

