**Table 3 Adverse Event Device Relationship**

Relationship	Description
Not Related	
 
• Not associated with the device
 
• due to an underlying or concurrent illness or effect of another device or drug
 

Unlikely	
 
• Little or no temporal relationship to the study device and/or
 
• a more likely alternative etiology exists
 

Possible	
 
• Temporal sequence between device application and event is such that the relationship is not unlikely or
 
• subject's condition or concomitant therapy could have caused the AE
 

Probable	
 
• Temporal sequence is relevant or
 
• Event abates upon device removal or
 
• event cannot be reasonable explained by the subject's condition
 

Highly Probable	
 
• temporal sequence is relevant and
 
• event abates upon device removal or
 
• reappearance of the event on repeat device application
 

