## 14.7 Additional Procedures, Pre-mature Explant, Device Replacement

As with any surgical procedure, additional procedures may be required in the event of an adverse event. The occurrence of complications may result in premature explant and/or replacement. Device replacement may be required if desired

volume is not achieved or if over-expansion leads to complications. Excess pressure may cause pain, ischemia, tissue injury or dehiscence of the wound if the pressure is not relieved.

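### Table 4 builds a non-pressure cause or condition into tissue damage, extrusion and erosion, so over-pressure injury, a hazard the protocol itself names, is left out of or mis-described in those event counts

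*Combined protocol and SAP*

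**What the plan says.** Section 14 opens by saying that adverse event data are collected under the definitions that follow, and the right-hand column of Table 4 is headed as definitions and criteria. Three rows carry a cause or a pressure condition:

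- Tissue damage: "Tissue thinning, necrosis, sloughing, (due to due to poor vascularization"
- Extrusion: "Extrusion at intended pressure, not wrinkle edge"
- Erosion: "Exposure of the implant despite a lack of excessive pressure"

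Elsewhere the protocol treats pressure as a cause of the same injuries. Section 14.7 says: "Excess pressure may cause pain, ischemia, tissue injury or dehiscence of the wound if the pressure is not relieved". The overfilling warning in 13.2.7 describes dosing past the labeled volume, or expanding too fast, as "possibly leading to discomfort, wound dehiscence, tissue damage or rupture of the expander". Section 13.2.8 repeats the tissue damage warning under Physician Expansion and adds compromised tissue integrity under Over-expansion/Rupture.

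Cause is meant to be judged separately. Section 14.1 has the investigator rate each event's relationship to the device using Table 3, and section 14.6 has a safety committee adjudicate relatedness for all adverse events.

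**The concern.** An event definition should say what was observed, and attribution should come afterwards. These three rows mix the two, and they do so on the mechanism that matters most for a gas-filled expander whose volume, once added, cannot be withdrawn in ordinary use. A site that applies the rows as written has no exposure row for an expander exposed by over-pressure. It can enter pressure necrosis as tissue damage only by also recording a vascular cause.

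The secondary safety measures in 4.2 cover device related and all adverse events. A reader of the safety tables will look at tissue damage, extrusion and erosion to judge whether expansion injures tissue. If pressure-caused cases sit under other headings, or sit under tissue damage with another cause attached, those lines do not answer the question.

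**Working it through.** The documents state no design figure on this point, so the check sets the texts side by side.

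**Step 1. Does each row admit a pressure-caused case?**

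| Finding caused by over-pressure | Table 4 row | Fits as written? |
|---|---|---|
| Thinning, necrosis, sloughing | Tissue damage | Only if pressure ischemia is read as poor vascularization |
| Expander exposed | Erosion | No, excess pressure must be absent |
| Expander extruded | Extrusion | No, pressure must be as intended |
| Open wound | Wound dehiscence | Yes, no cause condition |
| Unplanned surgery or removal in the operating room | Reoperation | Yes, "Any unplanned return to the operating room including device removal and/or replacement" |
| Anything else | Other | Yes, but worded as "Any other new sign or symptom that is reported by the subject during their enrollment in the study" and subject to the investigator's opinion |

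**Step 2. Is the event lost altogether?** No. Section 14.1 counts any untoward occurrence whatever its cause, and three rows remain open to it. What suffers is the count by event type.

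**Step 3. Does the row decide relatedness?** No text ties a Table 4 row to a Table 3 category. The one plausible path is that a form stating a vascular cause gives the rater a reason for Unlikely, because Table 3 allows that rating where "a more likely alternative etiology exists". This path exists only for cases entered in the tissue damage row. A case outside all three rows does not carry the label, and the extrusion and erosion conditions name no competing cause.

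**Step 4. Could primary failure change?** Section 4.1 has two routes to failure: a device related adverse event or a device malfunction. Table 5 lists over-expansion (altitude, operator overdose, valve failure) and rupture among potential device failures. What remains is pressure injury with no recognised malfunction, for example filling within the labeled volume but beyond tissue tolerance. There, failure status rests on the relatedness call.

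**Step 5. Scale only.** Inputs: up to 60 subjects (section 6), and 257 expanders (168 + 89) in 150 subjects in the earlier trial (section 1.4).

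- Expanders per subject: 257 / 150 = 1.713, which agrees with the stated bilateral rate (1.713 − 1 = 71%).
- Breasts, assuming the same mix: 60 × 1.713 = 102.8, about 103.
- One breast moved from failure to success: 1 / 103 = 1.0 point. If all subjects were unilateral, 1 / 60 = 1.7 points. If all were bilateral, 1 / 120 = 0.8 points.
- Illustration with an assumed 5 true failures: 98 / 103 = 95.1% (exact 95% interval 89.0 to 98.4). If 2 of the 5 were reclassified as successes: 100 / 103 = 97.1% (91.7 to 99.4). If those 2 were dropped from the denominator: 98 / 101 = 97.0%. The intervals treat breasts as independent.

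The counts of 5 and 2 are assumptions. Nothing in the documents says how many over-pressure removals to expect.

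**The case against.** A reader might infer that the wording pushes pressure injuries towards a finding of no device relationship and so inflates primary success. The documents do not support that.

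- Under section 14.3 a possible causal relationship is enough, and the Possible row of Table 3 accepts that the subject's own condition could have caused the event. An alternative cause alone does not take an event out of the device related group.
- A safety committee, with at least one physician who is neither an investigator nor a sponsor employee, adjudicates every adverse event. Photographs of breast events, returned expanders and controller logs are collected. The protocol does not say that the logs reach the committee, but that is a gap in description and does not show bias.
- Malfunction is a second route to failure, and section 14.8 calls any adverse event requiring replacement of the expander a treatment failure, with no relatedness condition.

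A reader might also infer that these events can be recorded only as Other. Wound dehiscence and Reoperation show otherwise.

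Two further objections are partly right. Section 14.5 introduces Table 4 as a summary of potential events, but the opening of section 14 and the column heading make it operative. Pressure ischemia can be read as poor vascularization, so the tissue damage row is not clearly closed to it. Even so, that reading merges a device hazard with the poor flap perfusion to which section 1.2 attributes typical complications.

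The objection therefore stands against any claim about the primary endpoint. It does not remove the defect in the event-type definitions.

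**Conclusion.** The definitions conflict with the protocol's own account of what excess pressure does. Counts of tissue damage, extrusion and erosion can omit, mis-describe or scatter pressure-caused cases. Overall adverse event and serious adverse event totals should be largely intact under section 14.1.

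An effect on device relatedness or primary failure is possible but not shown. It would be confined to pressure injury without a recognised malfunction, and it would also require the relatedness judgement to go wrong after adjudication. Its size cannot be computed from the documents. The figure of about 1.0 point per breast is a scale, not an estimate, and it assumes full enrolment and the earlier trial's mix of unilateral and bilateral procedures.

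The case report forms and the XPAND analysis plan, to which section 5.1 defers, were not available, so any coding rule or mechanism field there could not be checked.

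Separately, sections 4.1 and 14.8 differ on which removals or replacements are failures.

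**What to change.** - In Table 4, delete the vascular cause from tissue damage, the pressure condition from extrusion and the pressure condition from erosion, so that each is defined by the finding, as Wound dehiscence already is. When doing so, check that the remaining wording still tells extrusion and erosion apart by what is seen.
- Leave cause to Table 3 and the safety committee.
- Tabulate tissue damage, extrusion and erosion regardless of cause.
- Optionally, record suspected mechanism on the adverse event form if it is not already there.
- Reconcile sections 4.1 and 14.8 so that one rule states which removals and replacements count as failures.

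The cost is three phrases, one table specification and possibly one form field. Counts for these three event types may look slightly less favourable. No clinical management changes.
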